7.2.6. Criteria for Discontinuation of Dosing

Dosing will be required to be permanently discontinued (treatment discontinuation) for a subject if the subject experiences any of the events listed below following initiation of IP.

• SAE which is suspected of being related to IP, and study treatment continuation could present an unreasonable risk to the subject as determined by the Investigator, or Sponsor.

- Experiences a severe or serious (per Investigator assessment) opportunistic infection (suggestive of subject being immunocompromised)
- Receives a malignancy diagnosis, excluding carcinoma in situ of the cervix or squamous or basal cell carcinoma of the skin if it can be successfully treated by local resection
- Experiences an anaphylactic reaction or other severe systemic reaction (eg, hypersensitivity, allergic, or autoimmune) suspected of being related to IP by the Investigator or the Sponsor

- Experiences 2 separate occurrences of severe injection site reactions (ISR) that last longer than 24 hours.
 - A severe ISR is defined as an ISR that manifests with symptoms causing severe discomfort/pain; symptoms requiring medical/surgical attention/intervention; interference with activities of daily life (ADLs) including inability to perform daily social and functional activities (eg, absenteeism and/or bed rest); and/or when drug therapy is required
- Becomes pregnant
- Uses prohibited systemic immunosuppressive or immunomodulating drugs
- Uses systemic rescue therapy
- Misses 3 or more consecutive doses

These subjects will be encouraged to remain in the study and complete all required study assessments (which the exception of dosing with IP) remaining in the treatment period and follow up period of the study. In order to prevent missing data, the site staff will ensure attempts are made to reach subjects by phone or email that do not maintain contact with the Investigator. Any subject discontinuing the study prematurely will be asked to complete the ET Visit and the Initial and the Final Follow-up Visits.

Additional events that are considered sufficient reasons for discontinuing a subject from the IP are summarized in Section 11.1.

7.3. Method of Treatment Assignment

Subjects enrolled in the study will be centrally randomized on Day 1 after all screening and baseline assessments have been completed and the Investigator has verified that the subject is eligible per the inclusion (Section 4.2) and exclusion criteria (Section 4.3).

Subjects will be randomized (1:1:1:1) to receive either CC-93538 (mg QW, mg Q2W, or mg Q2W) or placebo for 16 weeks. Treatment assignment will be stratified by geographic region (Japan versus rest of world). Within the rest of world region only, randomization will also be stratified by disease severity based on the Day 1 baseline validated Investigator Global Assessment for Atopic Dermatitis (vIGA-AD) score (3 [moderate] or 4 [severe]). Randomization will occur on Day 1 (Baseline) through the use of Interactive Response Technology (IRT) system, also referred to as an Interactive Web Response System (IWRS) system.

Treatment groups are described in Section 7.2. The treatment each subject will receive will not be disclosed to the Investigator, study center personnel, subject, Sponsor or their representatives. The treatment codes will be held according to the IWRS. Further instructions will be provided in a separate IWRS manual.

The study blind should be maintained for persons responsible for the ongoing conduct of the study (after all subjects have completed the Week 16 assessments for endpoint analysis). Blinded persons may include but are not limited to: Clinical Research Physician (also referred to as Clinical Trial Physician), Clinical Research Scientist, Clinical Trial Manager, Study Statistician, Data Manager, Programmers, and Clinical Research Associates (CRAs). For details

of the emergency procedure for unblinding of individual subjects, see Section 11.4.

7.4. Packaging and Labeling

The label(s) for IP will include Sponsor name, address and telephone number, the protocol number, IP name, dosage form and strength (where applicable), amount of IP per container, lot number, expiry date (where applicable), medication identification/kit number, dosing instructions, storage conditions, and required caution statements and/or regulatory statements as applicable. Additional information may be included on the label as applicable per local regulations.

a label cover on the active and placebo syringes (to be applied during packaging/labeling) will be used to maintain the blind.

7.5. Investigational Product Accountability and Disposal

Celgene (or designee) will review with the Investigator and relevant site personnel the process for IP return, disposal, and/or destruction including responsibilities for the site versus Celgene (or designee).

All supplies of IP and placebo will be accounted for in accordance with GCP. There will be an individual IP accountability record for each subject and the Investigator should maintain accurate records relating to IP supplies received during the study. These records should include the amount of and dates clinical drug supplies were received, dispensed and administered to the subject by the investigative site or by a home healthcare service, or returned by the designated investigative site staff or by a home healthcare service and returned to the Sponsor. If errors or damages in the clinical drug supply shipments occur, the Investigator should contact the IP supplier and the Study Monitor immediately. Copies of the IP accountability records will be provided by each Investigator for inclusion in the Trial Master File after database lock. The Study Monitor will periodically check the supplies of IP held by the Investigator or pharmacist to verify accountability of all IP used.

The Investigator will provide IP only to the identified subjects of this study, according to the procedures described in this study protocol. After the end of the study, the Study Monitor will ensure that all unused IP and all medication containers, as applicable, can be destroyed on-site as long as proper documentation is supplied. If destruction on-site is not possible then any unused medication and containers, as applicable, will be returned to the Sponsor or designee. The Study Monitor will perform final accountability, package, seal and prepare for shipment. The clinical research organization (CRO) will verify that a final report of drug accountability is prepared and maintained in the Investigator Trial Master File.

7.6. Investigational Product Compliance

The Investigator must ensure that the IP will be used only in accordance with the protocol and that subjects are correctly instructed on how to take their IP and that each subject is fully compliant with their assigned dosage regimen. Investigational product non-compliance is defined as taking less than 80% or more than 120% of IP doses during the entire study. Records

of IP used and intervals between visits will be kept during the study. Drug accountability will be noted by the field monitor during site visits and at the completion of the study. The IP should be dispensed by the Investigator, or by a qualified individual under the Investigator's supervision. An up-to-date treatment inventory/dispensing record must be maintained.

8. CONCOMITANT MEDICATIONS AND PROCEDURES

All treatments (including prescription and over the counter [OTC] medications, herbal and dietary supplements, dietary modifications, and procedures) used by subjects within the 4 weeks (28 days) prior to the first Screening Visit or at any time during the study are regarded as prior or concomitant treatments and must be documented on the appropriate section of the eCRF. In addition, a history of previous treatments for AD will be documented.

All concomitant treatments, including blood and blood products, used from 28 days prior to the first Screening Visit until the Final Safety Follow-up Visit, or Final Study Visit must be reported on the eCRF.

8.1. Permitted Concomitant Medications and Procedures

The following concomitant medications are permitted during the study:

- Oral antihistamines are permitted; however, the dose and regimen should remain stable from at least 2 weeks prior to the Day 1 (Baseline) Week 16, EOT/ ET visit). Subjects should also refrain from dosing within 24 hours prior to a study visit.
- Subjects may use inhaled corticosteroids, leukotriene receptor antagonists (eg, montelukast), or mast cell stabilizers (eg, cromolyn sodium) for indications other than AD, such as asthma, if on stable doses/regimens for at least 4 weeks prior to the first Screening Visit and regimens should remain stable throughout the treatment duration of the study. If one of these medications was recently discontinued, it must have been discontinued at least 4 weeks prior to the first Screening Visit.
- Medically necessary dose adjustments (eg to treat unanticipated exacerbations, etc) will be permitted; however, changes should consistent with local treatment guidelines. In addition, the Medical Monitor should be consulted to discuss the potential impact of the medication changes.
- Ophthalmic corticosteroids are allowed for subjects receiving a stable dose to treat allergic conjunctivitis.

Unless prohibited, subjects may be administered any other medications necessary for the treatment of concurrent medical conditions or AEs, as deemed necessary by the Investigator. Following Day 1, addition of concomitant medications or any change in the dosage should be limited to those considered medically necessary.

8.2. Prohibited Concomitant Medications and Procedures

The introduction of medications or therapies for other medical conditions known to affect AD (eg, systemic corticosteroids, mycophenolate-mofetil, interferon gamma (IFN-y), Janus kinase inhibitors, biologic therapies, TCS (except when given for rescue therapy), TCI, cyclosporine, azathioprine, methotrexate, phototherapy, etc) are not permitted during the study.

Additional details related to the concomitant medications and procedures that are prohibited throughout the duration of the study are initially identified in the exclusion criteria (Section 4.3) are summarized below.

- Topical treatments that could affect the assessment AD (eg, corticosteroids, calcineurin inhibitors, tars, antibiotic creams, topical antihistamines) within 7 days of the Day 1 visit, and throughout the duration of study.
- Treatment with systemic antibiotics, antivirals, antiparasitics, antiprotozoals, or antifungals within 2 weeks prior to Day 1; however, during the study, use will be allowed to treat infection AEs.
- Phototherapy narrowband UVB (NB-UVB) or broad band phototherapy within 4 weeks prior to the baseline visit, and throughout the duration of the study.
- Systemic immunosuppressive or immunomodulating drugs (eg, azathioprine, cyclosporine, systemic corticosteroids, IFN-γ, Janus kinase inhibitors, methotrexate, mycophenolate-mofetil, etc.) within 4 weeks prior to the Baseline visit, and throughout the duration of the study.
- Treatment with immunomodulatory biologics as follows, and throughout the duration of the study:
 - Dupilumab within 3 months of Baseline visit.
 - Cell-depleting biologics, including to rituximab, within 6 months prior to the Baseline visit.
 - Other immunomodulatory biologics within 5 half-lives (if known) or 16 weeks prior to Baseline visit, whichever is longer
- With the exception of oral antihistamines, any additional medications and/or treatments that could affect AD are also prohibited throughout the study.
- Due to the potential to affect AD with ultraviolet light exposure, subjects must also avoid prolonged exposure to the sun and not to use tanning booths, sun lamps or other ultraviolet light sources during the study.
- Concurrent treatment with another IP, including through participation in an interventional trial for COVID-19 are prohibited throughout the duration of the study. Prospective subjects may not participate in a concurrent IP study or have received an IP within 5 drug half-lives prior to signing the ICF/assent for this study. Further, for subjects who received an investigational COVID-19 vaccine as part of a clinical trial prior to the first Screening Visit, enrollment must be delayed until the biologic impact of the vaccine is stabilized, as determined by discussion between the Investigator and the Clinical Trial Physician.
- Live attenuated vaccines are prohibited within one month prior to the first Screening Visit, and throughout the duration of the study.

8.3. Required Concomitant Medications and Procedures

Non-medicated topical emollient should be applied twice daily for \geq 7 days prior to the Baseline/Day 1 visit and application (at the same twice daily frequency) should continue throughout the study. On study visit days, subjects must not moisturize or apply emollient before the visit. The last application emollient should be applied the night before the planned

study visit. Non-medicated emollient is allowed after the visit is completed, and the same type of emollient should be used throughout the duration of the study.

8.4. Rescue Medication

In the event a subject develops intolerable AD symptoms that requires rescue therapy, exceptions related to prohibited medications, such as TCS use, will be permitted. The use of rescue therapy should be discouraged throughout the treatment phase of trial, and reserved for only severe symptoms associated with AD flares. In such cases, subjects may continue study participation, while continuing concomitant rescue therapy use; however, discontinuation of IP may be required depending on the type of rescue medication that is administered.

- Subjects requiring rescue therapy should consider the addition of TCS prior to considering systemic treatment. Any subject who requires TCS rescue therapy treatment are encouraged to continue the TCS for as brief a period as possible (eg less than 7 days), while continuing with treatment with IP, and maintaining the study visit schedule.
- Any subject requiring systemic rescue therapy to treat their AD during the treatment phase of the study will be discontinued from IP and will be encouraged to continue participation in the study without IP administration. Subjects who decline further participation in the study should proceed with the Early Termination Visit and follow up visit assessments. Subjects requiring systemic rescue therapy during the follow up period of the study should continue the study visits as planned. All instances of rescue therapy administration that occur during the course of study participation will be captured accordingly within the source documentation in the eCRF.

The impact of rescue therapy will also be evaluated by defining these endpoints as missing for subjects who initiate rescue therapy prior to Week 16 and analyzed according to methods described in Section 9.
9. STATISTICAL CONSIDERATIONS

9.1. Overview

This is a Phase 2, multicenter, global, randomized, double-blind, placebo-controlled, parallelgroup study to evaluate the safety and efficacy of CC-93538 in adult subjects with moderate to severe AD. Subjects will be randomized to receive study medication for 16 weeks and the randomization will be stratified by geographic region (Japan versus rest of world) and, within RoW region only, randomization will also be stratified by disease severity based on baseline vIGA-AD score (3 [moderate] or 4 [severe]). An independent DMC will be used to review the safety data regularly during the course of the study.

Analysis details not explained in the statistical section of the protocol will be provided in the Statistical Analysis Plan (SAP).

9.2. Study Population Definitions

The following analysis populations will be used in the statistical analysis:

Modified intent to treat (mITT) Population

All randomized participants who received at least 1 dose of IP.

The mITT population will be used as the primary population for all efficacy parameters. Subjects who prematurely withdraw from the trial for any reason and for whom an assessment is not performed for any reason will still be included in the mITT population. Subjects will be included in the treatment group to which they are randomized. Subjects who were randomized with a misreported stratum will be classified according to their original (misreported) stratum.

Safety Population

The Safety population will consist of all subjects who received at least one dose of IP. This population will be used for all summaries of safety data. Subjects randomized to placebo who receive any dose of CC-93538 will be summarized in the CC-93538 group. Subjects randomized to CC-93538 who receive only placebo will be summarized in the placebo group; otherwise, they will be summarized in the CC-93538 group.

Pharmacokinetic Population

All subjects who received at least one dose of active drug and have at least one measurable concentration data.

Biomarkers

All participants that received any study treatment and have any available biomarker measurement.

9.3. Sample Size and Power Considerations

Approximately 200 subjects will be randomized in this Phase 2 dose ranging study. Randomization will be equal among the 4 dose groups of placebo, mg Q2W, mg Q2W, and mg QW (approximately 50 subjects per group). Assuming a 10% dropout rate, a sample size of 45 subjects per group will provide approximately 90% power to detect a treatment difference relative to placebo (difference in means) of 35% with respect to the primary endpoint of percentage change from baseline in EASI scores at Week 16. In these power calculations superiority over placebo for a particular dose group is met if the lower bound of the (2-sided) 95% confidence interval (z-score) for the treatment difference exceeds zero (adjusted for multiplicity).

The sample size calculations are based on the following considerations for comparing mean percentage changes from baseline in EASI scores at Week 16 versus placebo. In particular, the recent Phase 2b study of dupilumab reported an observed mean for placebo of 18.1% and corresponding treatment differences of 50.1% (standard error [SE = 6.7%]) and 55.7% (SE = 6.7%), for the doses of 300 mg Q2W, and 300 mg QW, respectively (Thaci, 2016). This study evaluating CC-93538 is designed to detect a (true) treatment difference relative to placebo of 35%. We assume a (true) mean of 20% for placebo, and means for the active dose groups corresponding to treatment differences of 25% mg Q2W), 30% mg O2W), and 35%mg QW), with a common standard deviation (SD) of 50%. We note that the common SD assumption of 50% for the percentage change from baseline in EASI scores at Week 16 was also assumed in the dupilumab Phase 2b study design (Thaci, 2016). Under these assumptions, it is estimated that with a sample size of 45 subjects per group the study provides approximately 90% power to detect superiority relative to placebo for at least 1 dose at the overall type-1 error of α = 0.05 (two-sided) using a hierarchical testing approach (in the order of mg QW versus placebo. mg Q2W versus placebo, and mg Q2W versus placebo).

In addition, the study will provide more than 90% power to detect superiority relative to placebo for at least one dose with respect to the key secondary endpoint of vIGA-AD response (0-clear, 1-almost clear) at Week 16 assuming true proportions of 2% (placebo), 15% and 22W), 25% (mmg Q2W), and 25% mmg QW). We note that the Phase 2 dupilumab study reported proportions of 30% and 33% for the doses of 300 mg Q2W, and 300 mg QW, respectively (Thaçi, 2016). The hierarchical testing approach used for the primary endpoint was utilized to maintain the overall type-1 error of $\alpha = 0.05$ (two-sided) with respect to the IGA response endpoint. However, multiplicity adjustments are not implemented across endpoints jointly (eg, for both the primary and key secondary endpoints simultaneously).

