Tralokinumab when dosed at 300 mg every other week (Q2W) demonstrated superiority over placebo in all primary and secondary endpoints at Week 16. For the primary endpoint, an IGA 0/1 was achieved for subjects treated with tralokinumab was 15.8% for versus 7.1% for placebo in ECZTRA 1 and 22.2% versus 10.9% for ECZTRA 2. Reduction of the worst daily average of Pruritus Numeric Rating Scale (NRS) \geq 4 from baseline to Week 16 was 20.0% with tralokinumab versus 10.3% with placebo in ECZTRA 1 and by 25.0% versus 9.5% with placebo in ECZTRA 2. The overall frequency and severity of AEs over 16 weeks was comparable between tralokinumab and placebo. Of the most frequently reported AEs (\geq 5% in any treatment group), upper respiratory tract infection and conjunctivitis occurred more frequently with tralokinumab versus placebo, and dermatitis atopic and skin infection occurred more frequently with placebo (Wollenberg, 2020). Tralokinumab demonstrated in Phase 3 studies that targeting IL-13 alone in is both a safe and effective therapy; however, is the overall efficacy profile does not appear to be superior to biologic agents already on the market. When compared to the results

reported from dupilumab Phase 3 SOLO 1 and SOLO 2 induction studies, response rates for achieving IGA 0/1were as high as 38% to 36% in the dupilumab 300 mg Q2W arm, compared to 10% to 8% in subjects treated with placebo (Simpson, 2016). Although tralokinumab is anticipated to the first anti-IL-13 approved for the treatment of moderate to severe AD, there remains a need to further evaluate other biologic agents targeting IL-13 pathway, to further assess anti-IL-13's potential of achieving an optimized efficacy profile in subjects with moderate to severe AD.

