Phase 3 studies with lebrikizumab in AD are currently ongoing; therefore, it is too soon to tell if the efficacy profile observed in the Phase 2b study will be replicated in registrational programs. However, lebrikizumab's efficacy and safety profile observed in the high dose arm in Phase 2b are encouraging, and support the hypothesis that higher dosing with therapeutic agents targeting IL-13 may be able to provide improved disease outcomes for patients with AD.

CC-93538 will be the most recent anti-IL-13 mAb to be evaluated as a potential therapeutic option for subjects moderate to severe AD. Although CC-93538 shares a similar MOA to tralokinumab, as it prevents IL-13 binding to both IL-13R α 1 and IL-13R α 2 (Tripp, 2017), further research is needed to better understand the role of IL-13 R α 2 in atopic skin inflammation and fibrosis (Furue, 2020). As response rates in AD studies vary across the current biologic agents, clinical investigations with new therapies, like CC-93538, provide a unique opportunity to potentially optimize efficacy, by leveraging existing knowledge available from similar compounds.

The concept of

his Phase 2 dose ranging study to evaluate the potential of CC-93538 as a highly effective and well tolerated treatment option for AD.

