1.3.1.1. Benefit-Risk Assessment

As few advanced treatment options exist for patients with moderate to severe AD, there is an unmet need for new pharmacotherapies targeting the pathophysiology of AD with a safety and tolerability profile acceptable for long-term treatment. Based on the clinical safety and efficacy data with CC-93538 reported to date, the benefit-risk assessment of CC-93538 supports further development in AD and other inflammatory conditions.

CC-93538 a biologic immunomodulator targeting IL-13, was generally well tolerated in the Phase 2 study conducted in EoE subjects, without an increased risk of serious infection. Other immunomodulatory biologics in development or marketed for type 2 inflammatory diseases with a related mechanism of action, for example, dupilumab (targeting the IL-4 receptor, blocks IL-4R α (alone) and blocks IL-13/IL-13R α 1 signaling (Harb, 2020), lebrikizumab (targeting IL-13), and tralokinumab (targeting IL-13), also have not been associated with an increased risk of serious viral infections based on data observed in the extensive Phase 2 and Phase 3 clinical program. Although targeted corona virus disease (COVID) related research with these agents is limited, small studies conducted in patients with AD from high endemic areas (eg, Lombardy, Italy) provides supplemental, real-world evidence, that that there does not appear to be an increased risk for COVID 19 infection in patients being treated dupilumab (Carugno, 2020), which has a MOA similar to CC-93538.

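### Is the power of more than 90% stated for vIGA-AD 0/1 undermined by a 2% placebo response that has no stated source?

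*Combined protocol and SAP*

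**What the plan says.** After sizing the trial on percentage change in EASI, Section 9.3 adds that "the study will provide more than 90% power to detect superiority relative to placebo for at least one dose" on vIGA-AD 0/1. The inputs are "vIGA-AD response (0-clear, 1-almost clear) at Week 16 assuming true proportions of 2% (placebo), 15"% in the first-listed Q2W arm, then 25% in the other Q2W arm and 25% in the QW arm. The only outside figures given with it are active-arm rates: "the Phase 2 dupilumab study reported proportions of 30% and 33"% for dupilumab 300 mg Q2W and QW. For the primary endpoint the same section does give a placebo benchmark. It says the dupilumab Phase 2b study "reported an observed mean for placebo of 18.1"%, and it assumes 20%.

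Placebo IGA 0/1 rates appear only in Section 1.3.1. For tralokinumab against placebo they are "15.8% for versus 7.1% for placebo in ECZTRA 1 and 22.2% versus 10.9% for ECZTRA 2". For the dupilumab Phase 3 trials the response rates were "as high as 38% to 36% in the dupilumab 300 mg Q2W arm, compared to 10% to 8% in subjects treated with placebo". The protocol relates the compound to both drugs: in Section 1.3.1 "CC-93538 shares a similar MOA to tralokinumab", and Section 1.3.1.1 describes dupilumab as a treatment "which has a MOA similar to CC-93538".

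Section 9.6.2.1 tests the endpoint with a stratified CMH test at two-sided 5%, with missing values counted as non-response. The doses are taken in the same fixed order as for the primary endpoint, QW first. Differences in proportions with 95% confidence intervals are reported for every dose.

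**The concern.** The power claim depends heavily on the control rate, and that is the one input shown without support. All four placebo rates in the documents are 3.5 to 5.5 times the assumed 2% (7.1/2 = 3.55; 10.9/2 = 5.45). The responder definition does not explain the gap. Entry requires vIGA-AD of at least 3, so reaching 0 or 1 already means a drop of at least 2 points.

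If placebo response were near the cited rates and QW response stayed at 25%, the test would be far weaker than advertised. QW comes first in the sequence, so a miss there ends formal testing of both Q2W doses on this endpoint. A reader who trusts the stated power could then take a non-significant result as stronger evidence against the drug than it is.

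**Working it through.** **Which comparison the figure describes.** Under a fixed sequence at full alpha, power for at least one dose equals power of the first test, QW versus placebo. The other 25% arm adds nothing.

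**Inputs.** Placebo 2%, QW 25% (Section 9.3). Two-sided alpha 0.05. Either 50 per arm (as randomised, which fits mITT with missing values as non-response) or 45 per arm (the dropout-reduced count used for EASI).

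**Reproducing the stated figure, normal approximation.** Power = Φ[(p₂ − p₁ − 1.96·SE₀)/SE₁], with SE₀ = √[2p̄(1 − p̄)/n] and SE₁ = √[(p₁(1 − p₁) + p₂(1 − p₂))/n].

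- p̄ = (0.02 + 0.25)/2 = 0.135.
- n = 45: SE₀ = 0.0720, SE₁ = 0.0678, and (0.23 − 1.96 × 0.0720)/0.0678 = 1.309, so power is 0.905.
- n = 50: SE₀ = 0.0683, SE₁ = 0.0644, and (0.23 − 1.96 × 0.0683)/0.0644 = 1.492, so power is 0.932.

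**Exact version.** Sum the product of the two binomial probabilities over all outcomes (x on placebo, y on QW) for which the CMH statistic favours QW and exceeds 1.96. For a single stratum z = [(y − x)/n] / √[p̂(1 − p̂)(2/n)(2n/(2n − 1))], where p̂ = (x + y)/(2n). At 2% versus 25% this gives 0.948 (n = 45) and 0.967 (n = 50). The claim of more than 90% is met by both methods.

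**Sensitivity to the placebo rate, exact, n = 50 (n = 45 in brackets).**

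| Placebo rate | 25% active | 23-point difference kept |
|---|---|---|
| 3% | 0.934 (0.910) | – |
| 7.1% | 0.70 (0.67) | 0.87 (0.84) |
| 8% | 0.64 (0.61) | 0.85 (0.82) |
| 10% | 0.51 (0.48) | 0.82 (0.78) |
| 10.9% | 0.45 (0.43) | 0.81 (0.77) |

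With 25% active, power stays at 0.90 up to a placebo rate of about 3.8% (n = 50) or 3.2% (n = 45). At the active rates quoted in Section 9.3, power over the four cited placebo rates at n = 50 is 0.67 to 0.87 with 30% active and 0.78 to 0.925 with 33% active.

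**Complete pairs as cited, so that both rates come from one trial.**

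| Cited pair (placebo vs active) | n = 50 | n = 45 |
|---|---|---|
| Tralokinumab, 7.1% vs 15.8% | 0.27 | 0.25 |
| Tralokinumab, 10.9% vs 22.2% | 0.32 | 0.31 |
| Dupilumab Phase 3, 10% vs 38% | 0.928 | 0.898 |
| Dupilumab Phase 3, 8% vs 36% | 0.945 | 0.923 |

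Stratification matters little. In three-stratum CMH simulations with assumed splits of 20/40/40 and 10/60/30 across Japan, RoW score 3 and RoW score 4, power moved by no more than about 0.02.

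**Reading.** The low range of 0.45 to 0.70 pairs a placebo rate from one set of trials with an active rate that none of them reports beside it. Taken as complete pairs, the evidence runs from 0.27 to 0.945, and two of the four pairs support the stated figure at n = 50. In the tralokinumab pairs the active rates (15.8%, 22.2%) are also below 25%, so the placebo rate is not the only cause of the low power.

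**The case for a change.** The strongest case for a change is this. The protocol benchmarks placebo for EASI but not for vIGA-AD. Every placebo rate it prints is well above 2%. Nothing in the endpoint handling pulls the rate down, since rescue counts as non-response only in a sensitivity analysis. With 25% active and a cited placebo rate, the chance of missing on QW at n = 50 is about 30% to 55% (1 − 0.70 to 1 − 0.45), against under 10% implied by the stated power. Keeping the 23-point difference still leaves power below 0.90. The endpoint is formally tested, Section 1.3.2 treats it as informative about registration, and two or three sentences would repair the text.

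The omission and the sensitivity both stand. Two parts of the case do not. First, the input cannot be called wrong. The sentence after the 2% refers to the dupilumab Phase 2 study for this endpoint. Section 9.3 shows that study had a placebo arm, but its placebo IGA rate is not in the documents, so whether 2% matches it cannot be judged from here. Second, the consequence for the reader is limited. Observed differences with 95% confidence intervals show the precision of a non-significant result more directly than power computed beforehand. A QW miss ends only formal testing, and estimates and intervals for both Q2W doses are still reported.

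**Conclusion.** No change to the plan is needed. The stated power is a conditional statement with its inputs in plain view, and it reproduces (0.905 and 0.932 by normal approximation, 0.948 and 0.967 exactly, at 45 and 50 per arm). What is missing is background on one planning assumption.

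Supplying it would alter no sample size, test, endpoint status or reported result. The trial is sized on EASI, where 45 per arm with a 35-point difference and SD of 50 gives 91.3% against the stated approximately 90%. The vIGA-AD sentence is supplementary.

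Anyone using the figure should treat it as holding for placebo rates up to about 3% to 4% with 25% active. At placebo rates of 7.1% to 10.9%, power at 50 per arm is about 0.45 to 0.70 with 25% active and 0.81 to 0.87 with the 23-point difference kept. A source for the 2% and a sentence to that effect would be a courtesy to the reader. This conclusion assumes that the quoted rates already count missing values as non-response and that the cited trials are only a rough guide to this population.
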